2.7 Vulnerable Subjects

Children between the ages of 13-17 will be included in this research as the program to be evaluated is specifically designed as an intervention for adolescents with symptoms of depression. Assent will be obtained from all children under 18 for study enrollment unless legally emancipated or financially independent in accordance with CA state regulations and regulations of the state in which the minor resides.

3. Methods and Procedures

3.1 Procedure

Recruitment

Participants will be recruited through community sampling and provider- or healthcare system-facilitated community recruitment. Contract research organizations (CROs) and other referral-based recruitment companies may be used to contact potential participants, providers, and healthcare systems. Recruitment methods may include provider referral, media and social media ads and posts; online advertisement; flyers and other physical ads; word of mouth; and outreach to providers, community members, and potential participant pools (including but not limited to caregiver groups, youth groups, health-focused groups and organizations, schools, and healthcare systems).

Providers may be compensated at a rate of \$200/hour for time spent assessing preliminary patient eligibility and referring preliminarily eligible patients to Limbix for prescreening. Specifically, providers who are compensated will be asked to complete a review of study eligibility criteria and indicate whether their patient is potentially eligible for the study (Appendix 8). Assessments of preliminary eligibility can be completed via chart review or via discussion with the patient. Potentially eligible individuals will be directed to the study landing page.

Potential participants (and legal guardians, if applicable) will be directed to a web-based landing page where they will either self-assess preliminary eligibility using an abbreviated prescreening form or be asked to indicate whether they meet sets of eligibility criteria via a full prescreening form (Appendix 3). If potential participants completing the prescreening form indicate that they are ineligible, they will be directed to a list of

mental health resources (Appendix 4). Potential participants who are unsure about their eligibility can reach out to a research team member to discuss further or will be contacted by a research team member to determine potential eligibility.

Preliminarily eligible participants (and legal guardians) will then be prompted to schedule a videoconferencing session with a research coordinator in order to complete the consenting process. Potential participants who indicate that they are under the age of 18 will be prompted to provide contact information for a parent or caregiver, who will be contacted with information about the study and/or the scheduled videoconferencing session. They will be provided with a link to access a video presentation describing all study components, participant rights, and contents of the consent/assent form, and will be asked to view the video and answer comprehension questions embedded within it before the videoconferencing session. Potential participants (and legal guardians) who have not viewed the video prior to the videoconferencing session will view it during the session. If participants do not attend their scheduled videoconferencing appointment, they may be sent an email or SMS message allowing them to reschedule their appointment.

Consent, eligibility confirmation, and enrollment

At the videoconferencing session, potential participants (or legal guardians, if required) will confirm their identity by presenting an approved form of U.S. identification. They will be asked to reschedule their appointment if they are unable to do so. If participants under the age of 18 do not have their legal guardian present, they will also be asked to reschedule. Potential participants (and legal guardians) will then receive a brief overview of study components, during which they will respond to comprehension checks, and have the opportunity to clarify any questions or concerns. If participants (and legal guardians) did not watch the video presentation describing all study components provided before the videoconferencing session, they will watch the video during the videoconferencing session in place of this brief overview. Participants will be informed that they will be randomly assigned to either the SparkRx or the eUC only condition and will be provided with comprehensive information about the consent form and their rights as research participants (for details, see section 8.2). After providing their full names and email addresses, a Part 11 compliant electronic signature will be obtained from the participant (or legal guardian) to document consent. Documented e-assent will be obtained for participants under 18 years of age. Emancipated minors and/or minors who are financially independent will be allowed to provide informed consent in accordance with federal guidelines, CA state regulations, and regulations of the state in which the minor resides. Participants who turn 18 during their participation in the study will be asked to provide informed consent once they reach the age of majority.

Following consent, participants and legal guardians will be asked to provide their preferred email address, preferred phone number for receiving text messages, information about their mobile device, home address, current address (in case safety concerns arise), and emergency contact information. Participants will be required to provide the name and contact info for their healthcare provider. To confirm that providers are licensed in the U.S., research coordinators will search for the provider in the National Provider Identifier (NPI) records directory (<https://npiregistry.cms.hhs.gov/search>). If a participant is unable to provide their healthcare provider's contact info, or the research coordinator is unable to confirm the provider's NPI record, the participant will be asked to provide the information of another healthcare provider. If the participant is unable to do so, they will be instructed to reschedule the appointment to a time when they can provide another provider's information, or they will be deemed ineligible. Participants (or legal guardians) will be asked to sign a HIPAA release form to allow Limbix to contact their healthcare providers.

To confirm that participants are located in the United States, they will be asked to provide the Internet Protocol (IP) address of the device they are using during the videoconferencing session. Research staff will determine whether the IP address is located within the U.S. by entering it into a known lookup website. IP address lookup is generally accurate (>90%) for determining whether a device is located within or outside the U.S. However, because IP addresses are not perfect indicators of location, if participants insist that they are within the U.S. despite providing a non-U.S.-based IP address, the enrollment will continue with the provision

that further checks of IP address will be conducted using location information already collected through the secure web portal and app. Participants whose location cannot be confirmed to be within the U.S. will be dropped from the study, as safety cannot be appropriately monitored and ensured for these individuals.

A participant account in a secure web portal will be created with a username (user email addresses) and a temporary password. Potential participants will log in to the portal and will be instructed to change their password. In the portal, potential participants will complete two forms needed to determine eligibility: the PHQ-8 and the Medication Use Screener (see Appendix 1). Potential participants who do not meet criteria for participation based on the PHQ-8 (score < 5) or who do not wish to (or cannot) respond to the Medication Use Screener will be informed of their ineligibility and directed to mental health resources.

Participants and legal guardians (if applicable) will then be asked to verbally confirm that they meet each eligibility criterion. To ensure privacy, legal guardians will be asked to leave the room unless the participant indicates that they want their guardian present. After confirming eligibility with the participant, the legal guardian will be asked to return and confirm the eligibility of their child. Participants who report a history of suicidal ideation or self-harm urges will be prompted to complete a safety plan in collaboration with the research coordinator and/or study clinician (Appendix 5). If participants endorse active suicidal ideation with intent during this session, they will be directed to seek an emergency psychiatric evaluation for further assessment of their risk and appropriate intervention (see section 4.8.1). Participants (or legal guardians) who indicate ineligibility to participate due to any of the other eligibility criteria will be directed to alternative mental health resources and will be ineligible to continue with participation. Participants who are ineligible as a result of having an incompatible mobile device/operating system will be sent an email offering the opportunity to schedule another video session if their device/operating system changes. All eligible participants will be provided with a safety plan document and instructions for completing and using this safety plan document should it be necessary (Appendix 5). An emailed or text reminder to complete this plan may be sent following the consent session.

Participants will be asked to indicate in weekly participant symptom checks (PSCs; see Appendix 1) or to notify the study team if their treatment for symptoms of depression or any other health condition changes during the study, or if they participate in any other treatment/intervention research study. Participants will be encouraged to follow the advice of their doctor regarding all medical decisions. Participants will be told that this is a blinded study, meaning that most of the study staff with whom they interact after randomization will not know whether they received the SparkRx app or not. They will be provided with contact information if they need to reach out for app or web portal troubleshooting, or with questions about their participation in the study.

After eligibility is confirmed, an account for legal guardians (if applicable) in the secure web portal will be created with usernames (user email addresses), and legal guardians will be provided a temporary password to log in to change their password. Participants and legal guardians (if applicable) will be directed to complete baseline assessments in the secure web portal. Upon completion of baseline assessments, participants will be randomized (1:1) to either the SparkRx condition or the eUC only condition (see descriptions below). Randomization will be stratified by participant-reported antidepressant medication status ([yes, no] from the Medication Use Screener) and participant-reported baseline PHQ depression severity (low: PHQ-8 score <15; high: PHQ-8 score ≥15). Participants will receive instructions on how to download and log into their assigned mobile app. Following randomization and app download, the session will end. Additional information will be sent to participants via email.

Following the videoconferencing session, research coordinators will contact participants' healthcare provider offices and indicate that the patient has enrolled in this research study. If information is volunteered to the research coordinator that the participant is not a patient of the healthcare provider, the participant will be contacted to provide information for an alternative healthcare provider. As participant safety may be compromised in the absence of a known U.S.-based healthcare provider, participants will be dropped from the

study if contact information for an alternative healthcare provider is not obtained.

Intervention Period

SparkRx group: The SparkRx mobile program will be 5 weeks in duration and self-guided. The five modules in this program are each expected to take around 60 minutes to complete. Modules do not need to be completed in a single session but can be completed over the course of several days. Emergency resources for participants experiencing thoughts of suicide or self-harm will be available in the app. While participants can progress through the programs at their own pace, participants will be instructed to complete one module in the mobile app per week, and to complete the program within the 5-week intervention period. Participants will be prompted to complete weekly PHQ-8 and PSC in the mobile application. App notifications, text (SMS) and/or email messages may be sent to participants to encourage them to complete the weekly assessments (i.e., PHQ-8 and PSC). To encourage participants to engage with the app, automated app notifications will also be sent. For participants under 18 years of age, legal guardians may receive email and/or text notifications to complete proxy PHQ-8 and PSC assessments in the secure web portal.

eUC group: Participants will download a mobile app that contains no content, but that provides access to in-app weekly PHQ-8 and PSC assessments.

All participants will receive notifications (app notifications and SMS and/or email) to complete the PHQ-8 and PSC). For participants under 18 years of age, legal guardians may receive email and/or text notifications to complete proxy PHQ-8 and PSC assessments in the secure web portal .

Post-intervention period

After the 5-week intervention period, all participants will be sent links via email and/or text to complete post-intervention self-report questionnaires in the secure web portal. Participants may receive automated email and text reminders to complete the post-intervention questionnaires. A study coordinator may also contact participants (and legal guardians) who have not completed post-intervention questionnaires before they reach a 2 week deadline.

One month after the end of the intervention period, participants will be prompted to complete self-report questionnaires to evaluate sustained effects of the intervention on relevant outcomes. Participants may receive automated email and text reminders to complete the questionnaires. A study coordinator may contact participants (and legal guardians) who have not completed follow-up questionnaires before they reach a 2 week deadline. Participants who do not complete the one-month follow-up questionnaires within 2 weeks will be considered lost to follow-up.

If a participant chooses to withdraw from the study at any point or the participant is dropped from the study during the intervention period (5 weeks), access to the web portal and mobile app will be restricted at that time; otherwise access to the mobile app will be restricted at the end of week 5 and access to the web portal will be restricted after 1-month follow-up assessments have been completed or the participant is deemed lost to follow-up.

All relevant FDA requirements for the conduct of clinical trials will be followed, including registration on clinicaltrials.gov. Email and other notification templates are provided in Appendix 6.

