2.5 Inclusion Criteria

1. 13-21 years of age
2. PHQ-8 score ≥ 5 at eligibility screening
3. English fluency and literacy (participant and legal guardian, if applicable)
4. Access to a compatible smartphone (or other device) and operating system (i.e., capable of installing the app from the Google Play or Apple App Store; list will be provided on study website [app2]) and regular internet access
5. Participant willing and able to provide informed consent/assent and have legal guardian willing and able to provide informed consent (if required)
6. Under the care of a United States (U.S.)-based licensed healthcare provider and willing and able to provide contact information for the provider and sign a HIPAA release that allows Limbix to contact provider
7. Willing and able to provide information required for study enrollment (e.g. all responses to initial PHQ-8 assessment, and current antidepressant medication status)
8. Located in the continental U.S., Hawaii, or Alaska, and not planning to leave the U.S. during the study period (through 1-month follow up assessments, up to 11 weeks after eligibility screening)

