Study personnel will review all data collection materials on an ongoing basis for data completeness and accuracy as well as protocol adherence. Protocol deviations and violations will be reported in accordance with IRB and FDA guidelines. In this study, a protocol violation includes but is not limited to randomization of an ineligible participant and failure to obtain informed consent/assent. A protocol deviation includes but is not limited to minor deviations from protocol that do not impact safety or efficacy and failure to keep IRB approval up to date.

A formal Data and Safety Monitoring Board (DSMB) will be assembled in accordance with NIH and NIMH criteria to ensure that the safety of study subjects is protected and that the scientific goals of the study are being met. The team assembled for the DSMB will have relevant and complementary expertise in adolescent psychiatry, clinical trial design, digital health, and statistics. Specifically, the members of the DSMB will include a child psychiatrist with expertise in depression and related disorders, a biostatistician with expertise in clinical trial design and analysis, and an expert in digital health. Importantly, none of these individuals will be involved in any other capacity with this study or have any potential conflicts of interest in study-related outcomes. Additionally, an independent unblinded, non-voting statistician will review the validity of data summarized in reports provided to the DSMB and serve as a consultant during meetings.

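### U.S. location (for participants with a discordant IP address) and patient status with the named provider (for everyone) can be unverified at randomisation, and unresolved cases are dropped afterwards

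*Combined protocol and SAP*

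**What the plan says.** Section 2.5 sets two relevant conditions of entry. Inclusion 6 is "Under the care of a United States (U.S.)-based licensed healthcare provider and willing and able to provide contact information for the provider". Inclusion 8 is "Located in the continental U.S., Hawaii, or Alaska, and not planning to leave the U.S. during the study period".

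Section 3.1 describes one video session. Before randomisation, the participant (or guardian, if required) "will confirm their identity by presenting an approved form of U.S. identification", and addresses and an emergency contact are taken. The provider's licence is checked: "To confirm that providers are licensed in the U.S., research coordinators will search for the provider in the National Provider Identifier (NPI) records directory". Staff look up the IP address of the device in use, and participant and guardian confirm each criterion verbally. The section then treats eligibility as confirmed and moves to baseline assessments, 1:1 randomisation and app download: "Following randomization and app download, the session will end".

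Two matters are carried past that point.

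- **Location.** "if participants insist that they are within the U.S. despite providing a non-U.S.-based IP address, the enrollment will continue with the provision" that further IP checks are made through the portal and app. No deadline is given. If location cannot be confirmed, the participant is dropped.
- **Provider.** After the session, coordinators tell the provider's office that the patient has enrolled. "If information is volunteered to the research coordinator that the participant is not a patient of the healthcare provider", the participant is asked for another provider, and is dropped if none is obtained.

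Section 7.3 repeats both as grounds for ending participation. Section 3.1 also restricts portal and app access at once when someone is dropped during the 5-week period. Section 4.8.1 states that "a protocol violation includes but is not limited to randomization of an ineligible participant".

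**The concern.** Whether a participant is in the U.S., and whether the named clinician is really their provider, are facts that exist before allocation. If they are tested afterwards, a failed test becomes a drop from a randomised trial when it could have been a screen failure. The dropped person's later outcomes are then lost, because portal and app are closed to them.

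Safety is also at stake. Section 3.1 says safety cannot be properly monitored in people whose location is unconfirmed, and may be compromised where there is no known U.S. provider. The same section allows such people to be randomised and to start. Where the provider's office volunteers nothing, a person who is not its patient can stay in for the whole study.

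**Working it through.** **1. Place each check relative to randomisation (section 3.1).**

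| Check | When | Who | What it leaves open |
|---|---|---|---|
| U.S. identification | before | all (may be the guardian's) | shows identity, not current location |
| Addresses, verbal confirmation | before | all | self-report, which a discordant IP address calls into question |
| IP lookup | before | all | settles nothing when it is non-U.S. and the person insists |
| Further IP checks, portal and app | not tied to randomisation; app data can only come after it | discordant IP only | no deadline |
| NPI search | before | all | shows the provider is licensed, not that the participant is a patient |
| Contact with provider's office | after | all | passive: depends on volunteered information |

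The location gap therefore concerns only participants with a non-U.S. IP address who insist they are in the U.S. The provider gap concerns every participant, because the only outside source on patient status is contacted after the session and is not asked.

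**2. Set the consequences side by side.** Section 3.1 proceeds as though eligibility were confirmed, yet defers part of the confirmation. When a deferred check shows that the person never met inclusion 6 or 8, an ineligible participant has been randomised, which section 4.8.1 counts as a violation. Section 4.7.1 keeps all participants in their assigned arm. The current text does not say how these drops are handled in the analysis or whether they count against the attrition allowance.

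**3. Reproduce the sample size (section 4.6).** Inputs: d = 0.4, two-sided alpha 0.05, power 80%.

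- Normal approximation: n per arm = 2(1.960 + 0.842)² / 0.4² = 98.1, so 99. The exact t-test gives 99.08, so 100 per arm, as stated.
- Exact power at 100 per arm (noncentrality 0.4 × √50 = 2.83): 0.804.
- Enrolment: 200 × 1.10 = 220 as stated; 200 / 0.90 = 222.2, so 223. The difference is small.

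**4. Effect of extra drops on power.** The documents give no rate, so x is an assumed share of the 220 lost in addition to the 10% attrition. Evaluable N = 220 × (0.90 − x).

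| x | Extra drops | Evaluable N | Exact power |
|---|---|---|---|
| 0% | 0 | 198 | 0.800 |
| 1% | 2.2 | 195.8 | 0.795 |
| 2% | 4.4 | 193.6 | 0.791 |
| 5% | 11 | 187 | 0.777 |
| 10% | 22 | 176 | 0.751 |

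**5. How many could be flagged on location.** Section 3.1 puts IP lookup accuracy above 90%. If the error rate among genuine U.S. participants were 10%, 5% or 1%, then 220 × 0.10 = 22, 220 × 0.05 = 11 or 220 × 0.01 = 2.2 would show a non-U.S. address. These are eligible people who were looked up wrongly. They are not expected losses, and the number who are truly outside the U.S. is not given.

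**The case against.** The strongest reply is that the plan does check eligibility before allocation. Everyone has an IP lookup, everyone's provider must be found in the NPI directory or enrolment stops, and everyone confirms each criterion. This stands, and it limits the point to the two facts left open.

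A reader might infer more than the documents support:

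- **That both criteria are checked only after randomisation.** They are not, as the first table shows.
- **That following the procedure necessarily produces violations.** Section 4.8.1 concerns people who are in fact ineligible. A U.S. resident with a wrong lookup is eligible, and someone who named the wrong provider may supply another. The procedure permits a violation; it does not guarantee one.
- **That up to 22 participants could exhaust the attrition allowance of 220 − 200 = 20.** The 22 are flagged eligible people at an upper-bound error rate. Only those whose location stays unconfirmed are dropped.
- **That the ITT set shrinks.** Section 4.7.1 keeps everyone as assigned. What is lost is outcome data after the drop.
- **That detection differs by arm because SparkRx users spend more time in the app.** The IP flag is raised before allocation, both arms have an app with weekly assessments and the same portal, and nothing says detection depends on time in the app.

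It can also be objected that calling every provider before randomisation would split a single session and separate the screening PHQ-8, the baseline value, from allocation. That is right, and such a change is not proposed. Finally, portal data from the same session would probably come from the same connection and repeat the discordant result. This is why the fix relies on a rescheduled session.

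**Conclusion.** The point holds in this limited form. U.S. location, for participants with a discordant IP address, and actual patient status, for all participants, can be unverified at randomisation. Unresolved cases are then dropped for reasons that pre-date allocation. This fits poorly with section 3.1's own premise that eligibility is settled first, and it can lead to an ineligible person being randomised.

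The weight lies in safety, on the protocol's own statements, and in avoidable post-randomisation drops. Power is a minor matter: about 0.80 falling to 0.79 if 2% extra drops are assumed, and 0.777 at 5%. These rates are assumptions, since the documents give none for unconfirmed location or for wrongly named providers. No bias between arms is shown. The correction is cheap enough that it should be made.

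**What to change.** 1. **Section 3.1, location.** When the IP address is non-U.S., do not randomise in that session. Reschedule to one where U.S. location can be confirmed, for example from another connection or from portal location data. Section 3.1 already reschedules for missing identification or provider details. If location stays unresolved, record a screen failure.
2. **Section 3.1, provider.** In the call already made to the provider's office, ask whether the person is a current patient, to the extent the signed HIPAA release allows, and do not wait for this to be volunteered. The release is described only as permitting contact, so its scope needs checking. Do not require the call before randomisation for everyone.

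Cost: protocol wording and one added question. A small number of participants with discordant IP addresses will be delayed or lost before randomisation. Active questioning may identify a few more non-patients after randomisation; they stay in the ITT set as assigned.

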4.6 Sample Size

Sample size calculation is based on primary outcome PHQ-8 at post-intervention. Six PHQ-8 measurements will be collected from each subject (baseline and weekly during the 5-week intervention period). Using a two-sample t-test approach, assuming a two-tailed alpha set at 0.05, a total of 200 participants (100 in each study arm) will give us 80% power to detect a moderate effect size of at least $d=0.4$. Given an anticipated 10% rate of attrition, we aim to enroll 220 total participants in the study.

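### For minors who attend with a guardian, the PHQ-8 that sets eligibility, stratum and baseline is completed before the step at which the guardian is asked to leave for privacy

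*Combined protocol and SAP*

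**What the plan says.** All of the steps below are in section 3.1 (consent, eligibility confirmation and enrolment) unless another section is named.

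1. Guardian attendance is compulsory for minors: "If participants under the age of 18 do not have their legal guardian present, they will also be asked to reschedule". Emancipated or financially independent minors may consent for themselves.
2. After consent and portal log-in: "In the portal, potential participants will complete two forms needed to determine eligibility: the PHQ-8 and the Medication Use Screener".
3. Verbal confirmation of each eligibility criterion comes next, and the privacy step belongs to it: "To ensure privacy, legal guardians will be asked to leave the room unless the participant indicates that they want their guardian present". The guardian then returns to confirm the child's eligibility.
4. Once eligibility is confirmed: "Participants and legal guardians (if applicable) will be directed to complete baseline assessments in the secure web portal". No second request to leave is written. Randomisation and the app download follow in the same session.

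Table 1 (section 3.4) marks the participant PHQ-8 at eligibility screening and not at baseline, so the screening score is the only one before randomisation. It is used for the entry criterion (2.5), the stratum below or at/above 15 (3.1), the baseline covariate and the within-arm 5-point check (4.7.2), response and the 5-point reduction (4.2), and the rise-from-baseline limb of the deterioration rule (4.8.1).

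Later PHQ-8s are completed in the app each week, and in the portal through a sent link after the intervention and at follow-up (3.1, 3.4). Guardian attendance is not required for any of them.

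**The concern.** The plan accepts that a guardian in the room is a privacy problem when a minor answers eligibility questions, and provides an exit for that reason. As ordered, the exit covers the spoken check but not the symptom questionnaire completed just before it. The background sections give the same reason for care: 1.2.2 cites adolescents' worries about privacy and stigma, and 1.2.3 cites greater self-disclosure with digital formats.

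If a minor answers differently with a guardian present, the baseline is shifted relative to later scores for a non-clinical reason. Entry and stratum near their cut-offs can then be wrong, and any result computed as a change from that baseline carries the shift. The score cannot be collected again after randomisation, so the order of steps matters beforehand or not at all. The participant's GAD-7, BADS and PQ-LES-Q have a similar gap, because the guardian has returned by then.

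**Working it through.** **Planned sample size.** No figure in the plan is in dispute; this confirms the base. Inputs (section 4.6): "assuming a two-tailed alpha set at 0.05"; "a total of 200 participants (100 in each study arm) will give us 80% power"; d = 0.4; "Given an anticipated 10% rate of attrition, we aim to enroll 220 total participants in the study".
- n per arm = 2 × (1.960 + 0.842)² / 0.4² = 98.1, so 99; the exact t-test gives 99.08, so 100. Power at 100 per arm is 0.807 (normal) or 0.804 (t-test).
- 200 × 1.10 = 220; dividing instead, 200 / 0.90 = 222.2, so 223. The difference is small and has no bearing here.

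**Who is affected.** Section 2.3 aims at equal representation below and above 18, without a quota: 0.5 × 220 = about 110 participants, less any minors who consent for themselves.

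**Assumed shift.** The documents give none. Take k = 1 to 3 points of under-reporting by every minor at screening only, equally in both arms. Over-reporting gives the mirror image.

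**Cut-offs.** A minor with a true score from 5 to 4 + k is screened out: a score of 5 (k = 1), 5–6 (k = 2) or 5–7 (k = 3). A minor with a true score from 15 to 14 + k is placed in the low stratum: 15, 15–16 or 15–17.

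**Single-case examples.**
- Response: true 10, reported 8, later 5. True reduction 5/10 = 50%; recorded reduction 3/8 = 37.5%, a non-response.
- Deterioration: true 14, reported 12, later 17. True rise 3; recorded rise 5 with a score of at least 15, so the rule in 4.8.1 fires.

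**Whole-arm mean reduction.** Understatement = share of minors × k = 0.5 × 1 = 0.5 up to 0.5 × 3 = 1.5 points.

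**Simulation.** Assumptions not in the documents: 100 per arm, half minors, SD 5, correlation 0.5 between baseline and week 5, mean baseline 12, control reduction 3, true arm difference 2 (0 for the type I error column). There were 4,000 runs per scenario, with scores normal and untruncated, no entry cut, and a baseline-adjusted comparison of the week-5 score standing in for the mixed model.

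| k | Type I error | Estimated arm difference | Power | Mean SparkRx reduction | SparkRx rate of ≥5-point reduction | Arm difference in that rate | SparkRx remission |
|---|---|---|---|---|---|---|---|
| 0 | 0.045 | −1.98 | 0.89 | 4.99 | 0.50 | 0.154 | 0.344 |
| 1 | 0.044 | −2.00 | 0.90 | 4.49 | 0.46 | 0.151 | 0.345 |
| 2 | 0.054 | −2.00 | 0.90 | 4.00 | 0.42 | 0.145 | 0.345 |
| 3 | 0.048 | −2.01 | 0.90 | 3.50 | 0.39 | 0.136 | 0.346 |

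**Effect on the 4.7.2 check.** On the same assumptions the variance of the change is 25 + 25 − 2 × 0.5 × 25 = 25. Shifting a random half by k adds 0.25k². The half-width is 1.96 × √(25 + 0.25k²) / √100 = 0.98 at k = 0 and 1.02 at k = 3. The 95% intervals are about 4.0–6.0 (k = 0), 3.5–5.5 (k = 1), 3.0–5.0 (k = 2) and 2.5–4.5 (k = 3). The interval contains 5 at k = 0 and 1, is on the edge at k = 2, and misses 5 at k = 3.

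**The case against.** The strongest reply is that guardian influence is inferred. Nothing in the documents says a guardian sees, helps with or supervises the screening PHQ-8. It is self-completed under the participant's own log-in, the guardian's account is created only later, and attending a video session is not the same as viewing the screen. Section 5 recommends a private location for research activities. Nor are later scores shown to be free of influence: guardians may be prompted for weekly proxy reports (3.1), and families are told at consent that guardians will be contacted if a minor seems to worsen (8.2).

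Most of this stands. A reader might infer that supervised baselines are being compared with unsupervised follow-ups; the documents establish only that attendance is required for the first and not for the rest. What remains is that a personal log-in does not control who is in the room, and general advice on privacy cannot exclude someone whose attendance is compulsory.

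It is also fair to say that the main inference is safe. The shift precedes allocation and is common to both arms, and remission uses no baseline. Three further inferences are tempting but unsupported:
- **The planned age-moderation analysis is distorted.** Section 4.7.4 asks whether age alters the intervention effect on the post-intervention score. A pre-randomisation shift in minors is on average equal in both arms, and an age main effect would absorb it.
- **A stable minor is flagged as deteriorating.** With a shift of at most 3 points, the 5-point rise also needs at least 2 points of real change.
- **The guardian's proxy ratings are contaminated.** This requires the guardian to have seen the answers, which nothing states.

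**Conclusion.** The point holds as a gap in the order of steps for participants under 18 who attend with a guardian: the existing privacy step comes after the one PHQ-8 it would most usefully protect. It is a cheap improvement and does not show a flaw in the primary comparison.

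The primary between-arm test and remission are not biased. A misassigned stratum is fixed before allocation and does not bias the arm contrast either. The exposed results are those listed in the brief; the arm difference in the 5-point rate is only slightly attenuated (0.154 to 0.136 at the extreme of the assumed range). Under the assumptions shown, the within-arm check in 4.7.2 can change its answer at 2 to 3 points of universal under-reporting among minors, but not at 1 point.

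These sizes rest on an assumed shift, an assumed half share of minors and assumed PHQ-8 variability. Neither the size nor the direction of any shift can be learned from the documents.

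**What to change.** In section 3.1:

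1. Move the existing request that the guardian leave so that it precedes the participant's opening of the PHQ-8 and Medication Use Screener.
2. Keep the guardian out through the participant's verbal eligibility check, with the same exception if the participant wants the guardian there. The guardian then returns to confirm eligibility, as now.
3. After that, ask participant and guardian to complete their baseline forms separately, with the guardian out of view of the participant's screen. A single exit lasting through all baseline forms would not fit, because those forms start only after the guardian has confirmed eligibility.

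Cost: small edits to the protocol text and the coordinator script, a slightly longer guardian absence, and one further request for separation in the same session. No extra visit, staff or form is needed.
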